Concomitant use of other drugs that inhibit CYP3A4 or CYP2C19 with clopidogrel may reduce the expected positive effects of treatment and induce negative ones, since the hepatic metabolism of clopidogrel is also mainly mediated by CYP2C19 and to a lesser extent by CYP3A4. The concomitant use of drugs that inhibit CYP3A4 or CYP2C19 can be assessed by reviewing the patient's medical history. Their use is prohibited during the study and must be discontinued 2 weeks before enrollment, otherwise, it will constitute an exclusion criterion from the study. Below is a list of drugs that inhibit CYP3A4 or CYP2C19 and their use is prohibited during the study period. If the use of these medications is necessary, the patient will be considered for withdrawal from the study.

— CYP3A4 inhibitors:

Omeprazole, clarithromycin, erythromycin, diltiazem, itraconazole, ketoconazole, ritonavir, verapamil, grapefruit;

— CYP2C19 inhibitors:

Omeprazole, fluvoxamine, ticlopidine, efavirenz, chloramphenicol, fluoxetine, delavirdine, gemfibrozil, stiripentol, bortezomib.

The PPI of choice for patients included in the study is pantoprazole. However, according to the CPIC CYP2C19 genotype-based PPI dosing guidelines and recommendations [25], carriers of CYP2C19 \*2, \*3 LOF alleles are at increased plasma concentrations of this PPI and increased risk of toxicity with prolonged treatment (>12 weeks). Despite the expected increase in treatment efficacy, the drug dose should be reduced by 50% for use >12 weeks and continued monitoring for maintenance of efficacy.

BMI is determined by calculating the results of simple anthropometry.  $BMI \geq 40 \text{ kg/m}^2$  defines clinical obesity/fatty states. They are considered an independent risk factor for repeated MACCE in CAD cases. Prevention of this risk factor requires consistent, intensive measures of lifestyle changes (diet, physical activity) and drug treatment for at least 6-12 months, during which it is impossible to achieve results during the study inclusion and observation period. The excess of risks due to this factor during the study may be an important reason for the dispersion of the study effects. Including patients with this clinical characteristic in the study group, only with the drug treatment provided by the study, would be ethically unjustified. Accordingly,  $BMI \geq 40 \text{ kg/m}^2$  is an important exclusion criterion from the study.

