Type 1 Diabetes mellitus and uncontrolled or poorly controlled type 2 diabetes mellitus are considered important independent risk factors for recurrent MACCE in CAD cases. High glycemia levels will act as an important cause of excess risk and may cause dispersion of effects in the course of the study.

Additionally, randomization of study participants with uncontrolled glycemia without CYP2C19 genotyping (control arm) and the possible presence of CYP2C19 \*2, \*3 LOF allele genotype cannot be assessed. Such study participants will be at higher risk than participants randomized in experimental arms, which would be unjustified, allow unequal risk in the study and raise ethical concerns.

Clinical evidence of Type 1 Diabetes mellitus can be assessed by obtaining the patient's medical history. Uncontrolled or poorly controlled diabetes mellitus can be specifically defined as a history of diabetes mellitus, clinical evidence of inadequate glycemic control, elevated glycated hemoglobin ( $HbA1c \geq 9\%$ ), or clinical evidence of vascular complications of diabetes.

Patients with type 2 diabetes mellitus may be included in the study if the results of the screening test:

- $HbA1c < 9\%$ ;  
[and]  
▪ are receiving optimal medical treatment to control glycemic levels;  
[and]  
have no evidence of progressive vascular complications of diabetes other than CAD;

Such assessment results should also be demonstrated by the 6th and 12-month follow-up of the study. If these key criteria for diabetes control are not met, the subject should be withdrawn from the study early after appropriate investigations have been conducted.

Acute myocardial infarction, valvular heart disease, or previous valvular heart surgery are high-risk conditions for recurrent MACCE.

Interstitial lung disease, neurodegenerative diseases, agranulocytosis (leukopenia, lymphopenia), pancytopenia, thrombocytopenia or thrombocytosis, and any other uncontrolled disease or clinical condition in the course of CAD are associated with high risks of other serious clinical conditions and a poor prognosis.

These diseases/conditions may serve as important causes of biases and confounding effects during analyzing study outcomes. They can be easily identified as part of screening measures based on the patient's medical history and the results of routine clinical examinations.

Certain conditions should be routinely considered for the determination of study exclusion criteria.

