## **3.3 Early Withdrawal of a Study Participant**

A study participant may withdraw from the study at any time during the study and for any reason, whether identifiable or not, by their own free will. This decision and the patient's independent choice are presented in the informed consent form.

A study participant may also be withdrawn early from the study if there is persistent non-adherence to the study follow-up and treatment procedures (see Chapter 2.5.6, Withdrawal from the Study Due to Non-Adherence to Treatment).

A study participant may be withdrawn early from the study based on a clearly stated justification by the investigator or the study sponsor if it is in the patient's best interests to discontinue the study.

The basic reasons for withdrawal from the study are considered as follows:

- If any abnormal study result, symptom, or measurement parameter is detected and resolution, improvement, correction or stabilization of which may require a long period of treatment and/or observation and will change the course of the study-defined follow-up and treatment;
- Any adverse event that may persist during the follow-up period, or require a change or discontinuation of the study-defined treatment, or disrupt the study-defined clinical evaluation plan, or be associated with a severe outcome.
- Any adverse event that may be masked by the use of different medical care regimens than those specified in the study protocol;
- If study treatment intervention, it may pose an expected AAME, a health threat, requiring discontinuation and modification. These conditions require modified treatment measures and regimens other than those specified in the study, including hospitalization. In addition, clinical conditions that may be characteristic of AAME may be exclusion criteria from the study.
- An adverse event related to treatment with P2Y12 inhibitors is a study endpoint, after which the study-planned follow-up is no longer required.
- The MACCE determines the study endpoint, and further measures are no longer required.

In these cases, study participants are discontinued from the study-planned follow-up; the necessary assessments of early withdrawal from the study should be conducted, and the reason for early withdrawal from the study should be determined (evaluated). In these cases, the patient continues to be monitored and treated by the medical support team.

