### **3.4 Definition of Study Completion**

The expected end of the study for a participant is determined by the date at the end of the 12-month follow-up period. However, in cases of early withdrawal, this period may be shorter.

Generally, the end of the study is determined by the end of the 12-month follow-up period for the last subject in the study.

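### Re-applying the diabetes entry criteria at month 6 ends endpoint follow-up early in participants the protocol regards as at higher risk

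*Combined protocol and SAP*

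**What the plan says.** Section 2.4.4 admits patients with type 2 diabetes on three conditions: HbA1c below 9%, optimal medical treatment of glycaemia, and that they "have no evidence of progressive vascular complications of diabetes other than CAD". It carries these conditions past randomisation: "Such assessment results should also be demonstrated by the 6th and 12-month follow-up of the study". It then states: "If these key criteria for diabetes control are not met, the subject should be withdrawn from the study early". The same section says that type 1 diabetes and uncontrolled or poorly controlled type 2 diabetes are "considered important independent risk factors for recurrent MACCE in CAD cases". For prohibited CYP3A4 or CYP2C19 inhibitors the wording is softer: "If the use of these medications is necessary, the patient will be considered for withdrawal from the study".

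The consequences of withdrawal are set elsewhere:

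- After its list of withdrawal reasons, Section 3.3 says: "In these cases, study participants are discontinued from the study-planned follow-up". Later monitoring passes to the medical support team, and the study uses the data gathered up to withdrawal.
- Section 3.4 ends participation at month 12 and adds: "However, in cases of early withdrawal, this period may be shorter".
- The Follow-up row of the Synopsis provides one evaluation within 72 hours of early withdrawal.
- Appendix 2 schedules HbA1c at screening, months 6 and 12, and withdrawal. It schedules endpoint evaluation at months 3, 6 and 12 and at withdrawal.

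Section 2.6.1 counts the primary and secondary endpoints over 12 months. Appendix 3 divides events by all participants in the arm. The plan states no intention-to-treat set, no censoring rule and no missing-data method.

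**The concern.** An eligibility condition is measured again after randomisation and used to end participation. On the protocol's own account, those who fail it are at raised risk of the outcomes being counted, so the loss is informative. After a month-6 failure, later deaths, infarctions, strokes and bleeds are not collected, yet the patient stays in the Appendix 3 denominator as if event-free.

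Two things are at stake. The first is the level of the event rates, which is pulled down. The second is the randomised comparison, which moves if the share withdrawn, or the excess risk of those withdrawn, differs between the genotype-guided and control groups. A difference is conceivable: Section 2.5.4 discloses the results to participants and the care team, and two of the three triggers (optimal treatment, progressive complications) rest on judgement.

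This rule is separate from the one in Section 3.2.6 that withdraws participants after a MACCE or AAME. A correction confined to that rule would leave this one in place.

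**Working it through.** The plan gives no figure for how many participants would fail these criteria, so there is no stated value to reproduce. Section 2.4.2 expects 75% to complete, which leaves 240 x 0.25 = 60 non-completers, but it does not attribute any of them to this rule.

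**Step 1: which check costs follow-up time.** The endpoint window is 12 months.
- Failure at month 6: 12 - 6 = 6 months lost.
- Failure at month 12: 12 - 12 = 0 months lost.

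Only the month-6 check removes endpoint time.

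**Step 2: participants affected.** Assumptions: 20-40% have type 2 diabetes, and 10-20% of those fail a criterion.
- Low: 240 x 0.20 x 0.10 = 4.8 (2%).
- High: 240 x 0.40 x 0.20 = 19.2 (8%).

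This is an upper bound on those cut off, because some failures would first appear at month 12.

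**Step 3: deaths lost.** Assumption: 12-month mortality of 1-2%, i.e. 2.4-4.8 deaths among 240, with half of the risk falling in months 6-12.
- Average risk: 4.8 x 0.01 x 0.5 = 0.02 to 19.2 x 0.02 x 0.5 = 0.19.
- Three times that risk: 0.07 to 0.58.

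**Step 4: share of all 12-month events lost.** Let f be the share withdrawn at month 6 and h their risk relative to the others, with a constant hazard. Share lost = 0.5fh / (1 - f + fh).
- f = 0.02, h = 1.5: 0.015 / 1.01 = 1.5%.
- f = 0.08, h = 3: 0.12 / 1.16 = 10.3%.
- At a wider assumed f of 0.05 to 0.15: 0.0375 / 1.025 = 3.7% (h = 1.5) to 0.225 / 1.30 = 17.3% (h = 3).

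Section 3.2.1 puts the probability of a MACCE, broadly defined, at 1-10%. Taking 10% as the 12-month risk in the others, the events lost are 240 x 0.02 x 0.10 x 1.5 x 0.5 = 0.36 to 240 x 0.08 x 0.10 x 3 x 0.5 = 2.9. At 1% they are a tenth of that.

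**Step 5: comparison between arms.** Let F be the share failing and w the share actually withdrawn. An arm's observed rate is proportional to 1 - F + Fh - 0.5wh.

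| Setting | True RR | Observed RR |
|---|---|---|
| Same F, h and w in both arms | 1 | 1 |
| F = 0.08, h = 2, w = 0.08 vs 0.02 | 1 | 1.00/1.06 = 0.94 (reversed: 1.06) |
| F = 0.15, h = 2, w = 0.15 vs 0.05 | 1 | 1.00/1.10 = 0.91 (reversed: 1.10) |
| F = 0.15, h = 3, w = 0.15 vs 0.05 | 1 | 1.075/1.225 = 0.88 (reversed: 1.14) |
| F = w = 0.08 in both arms; h = 2 experimental, 3 control | 1.08/1.16 = 0.93 | 1.00/1.04 = 0.96 |

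All values of F, h and w are illustrative; none is in the documents. The last row reflects the statement in Section 2.4.4 that participants with uncontrolled glycaemia in the ungenotyped control arm would be at higher risk than those in the experimental arms. Under that premise even equal withdrawal moves the ratio, here towards 1.

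**The case against.** The strongest reply has four parts.

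First, the plan handles withdrawal in part. The 72-hour evaluation, with endpoint assessment in Appendix 2, captures events up to that point. Section 2.4.2 anticipates non-completion and treats assessed dropouts as a data source, and Section 2.6.3 names Cox regression, which can censor. This stands for events before withdrawal. It does not recover later ones, and ordinary censoring does not correct loss that depends on risk. Appendix 3 in any case computes its hazard ratios as ratios of proportions.

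Second, nothing in the documents suggests that the choice of P2Y12 inhibitor changes HbA1c, so withdrawal may be balanced. This stands: with equal withdrawal, equal excess risk and no true effect the ratio does not move. Bias between arms is conditional, and a reader who infers that the randomised comparison is broken goes further than the text allows.

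Third, the vascular trigger excludes CAD. This also stands. Infarction, angina and revascularisation are not this trigger; among the listed endpoints, stroke or TIA is the plausible overlap.

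Fourth, the root cause is the general text of Sections 3.3 and 3.4, which equates withdrawal with the end of follow-up. Section 3.3 lists an abnormal measurement needing prolonged treatment or observation as a reason, so a raised HbA1c could still lead to withdrawal after Section 2.4.4 is reworded. This is right. It is a reason to widen the correction, not to drop the point.

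**Conclusion.** The point holds within limits. The plan directs withdrawal when the diabetes criteria fail, and nothing in it collects endpoints afterwards beyond one evaluation within 72 hours. A month-6 failure therefore costs about six months of follow-up in patients at raised risk, and the Appendix 3 rates are understated.

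On the assumptions of 20-40% with diabetes and 10-20% of those failing, at most 5-19 of 240 participants are affected and about 1.5-10% of 12-month events are lost (risk 1.5-3 times that of the others, constant hazard). Expected deaths lost are below one even at triple risk and 2% mortality, so the loss falls mainly on secondary and composite events. The size and direction of any bias between arms cannot be derived from the documents.

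A reader might infer more than this. Four such readings are not supported:
- That the month-12 check also removes endpoints. It comes when follow-up is complete and can only add to the count of withdrawals.
- That withdrawal is absolute and removes the highest-risk patients. The text says should, and it supports higher risk only.
- That a death is likely to be lost. The expected number is a fraction of one.
- That users of prohibited inhibitors are always withdrawn. Section 2.4.4 only has them considered for it.

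**What to change.** In Section 2.4.4, and in the follow-up text of Sections 3.3 and 3.4 and the Synopsis, separate stopping study procedures from stopping endpoint ascertainment. When a diabetes criterion is not met, record the finding and its date. Continue to collect vital status and all endpoints to month 12 for every randomised participant who has not withdrawn consent, including those who start a prohibited inhibitor. In Section 2.6.3, state that these participants are analysed in the group to which they were randomised, with events to month 12 counted.

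Reconcile the withdrawal reasons. The Synopsis lists four and does not name the diabetes criteria, which could enter only as a physician's decision; Section 2.4.4 names them; Section 3.3 covers them only through its general wording on abnormal measurements. Decisions on the care of these patients stay with the treating team and are not affected by this change.

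The cost is small: a wording change, the IRB review that Section 6.0 requires for any protocol change, a check that the consent form covers continued contact, and follow-up of an estimated 19 or fewer participants at the 12-month visit already in Appendix 2.

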## 2.5 Study Procedures

### 2.5.1 Screening

All patients

- must present having undergone ePCI within the past 12 weeks, documented by imaging and a report form,

[or]

- a practical clinical task must be defined to de-escalate antiplatelet therapy from an alternative P2Y12 inhibitor to clopidogrel or initiate clopidogrel.

eICA data must meet the criteria for CAD, and ePCI results must determine the indication for treatment with clopidogrel or an alternative P2Y12 inhibitor:

- Coronary artery stenosis;

[and]

- Coronary artery stenting with DES;

Study subjects must have formally confirmed informed consent to participate in the study, as approved by the ethics committee.

Study subjects should undergo baseline clinical assessments that will determine:

- Demography data:
  - Sex; Age; Race, Ethnicity, Country of residence.
- Cardiometabolic risk factors and their control status:
  - BMI; Obesity; Systolic and Diastolic Blood Pressure, Hypertension; T2 Diabetes Mellitus; HbA1c Measures; LDL-C, Dyslipidemia;
- History of Cardiovascular Morbidity. The patient must undergo all clinical-diagnostic examinations that confirm inclusion criteria and deny exclusion criteria:
  - Clinical indications for the most recent PCI;

- Angina
- No Angina: Heart Failure Event, Supraventricular Tachycardia, Atrial Fibrillation, Premature Ventricular Complex or Ventricular tachycardia, Left Bundle Branch Block;
- Other non-specific symptoms;
- History of any Cardiovascular Morbidity and their control status:
  - Prior Myocardium Infarction, Number of Prior MIs; Chronic Heart Failure; Supraventricular Tachycardia; Atrial Fibrillation; Premature Ventricular Complex; Ventricular Tachycardia; Ventricular Fibrillation Event; Sinus Node Dysfunction; AV Block; Left Bundle Branch Block; Right Bundle Branch Block; Coronary artery bypass graft;
- History of prior PCI:
  - Number of prior PCIs; Number of Coronary Artery Lesion Sites – total and obstructive; Number of Stents Ever Placed; Sites of Coronary Artery Lesions – obstructive and non-obstructive
- History of Co-morbid Diseases/Conditions and their control status. The patient must undergo all clinical-diagnostic examinations that confirm inclusion criteria and deny exclusion criteria:
  - Peripheral Artery Disease; Carotid Artery Disease; Cerebrovascular Disease;
  - Other co-morbid diseases/conditions:
    - Chronic Obstructive Pulmonary Disease; Chronic Kidney Disease; Peptic Ulcer Disease/Chronic Gastritis; GI Bleeding Event; Cured Cancer; Thyroid Disease
- Doppler-, Echocardiography characteristics of heart remodeling:
  - Left ventricle
    - PW, IVS thickness; Hypertrophy; Relative Wall Thickness; end-diastolic diameter; end-diastolic volume index; Mass index; Ejection fraction; Filling pressure;
  - Left atrium
    - transverse diameter; volume index;
  - Right Ventricular
    - Diameter, Dilatation; Pulmonary Artery Systolic Pressure (PASP); Tricuspid annular plane systolic excursion (TAPSE);
  - Mitral, Aortic, Tricuspid valve disorders
    - Mitral annular calcification (MAC); Secondary (functional) mitral regurgitation (FMR); Aortic valve calcification; Secondary (functional) aortic regurgitation (FAoR); Secondary (functional) Tricuspid Regurgitation (FTR).
- Ongoing medication treatment application:
  - Antiplatelet Treatment Selection:
    - DAPT; TRIPLE; Combined; Monotherapy
  - Antiplatelet Medications:
    - Aspirin; Clopidogrel; P2Y12 inhibitor, Alternative of Clopidogrel; NOAC;
  - Lipid-lowering Medications:
    - STATIN; STATIN plus EZETIMIBE; STATIN plus EZETIMIBE plus PCSK9i;
  - Hypoglycemic Medications:
    - Insulin; SGLT-2; Metformin; GLP1-AG; DPP4;
  - Other Medications:
    - ACEi; ARB; ARNI; Beta-Blocker; Calcium Channel Blocker; Anti-arrhythmics; Ivabradine; Loop Diuretic; Thiazide Diuretic; MCRA

Clinical examinations conducted as part of screening should not identify diseases/conditions included in the exclusion criteria (see Chapter 2.4.4 Exclusion criteria) or their specific laboratory and instrumental investigation findings:

- Complete blood count should not reveal:
  - Clinically significant anemia - Hb<10g/dl; RBC<3.5; HCT<32L/L;
  - Leukopenia - <3.0 x 10^9/L, or neutropenia - ≤1.5 x 10^9/L;
  - Lymphopenia - <1.1 x 10^9/L;
  - Thrombocytopenia - <100×10^9/L or <50% compared to previous measurement;
  - Thrombocytosis - ≥500×10^9/L;
- Coagulation tests should not reveal:
  - Thrombocytopenia - < 100×10^9/L or <50% compared to previous measurement data;
  - Prolongation of APTT - >45'';
  - Prolongation of PT - >16''
  - Prolongation of TT - >19'';
  - Decreased fibrinogen level - <200mg/dl or <50% compared to previous measurement data;
  - Hypocalcemia ionized calcium (iCa) < 0.89 mM/L;
- Blood biochemical tests should not reveal:
  - Hba1c ≥ 9%, in patients with type 2 diabetes;
  - eGFR ≤30% (according to the MDRD formula for kidney disease) or creatinine > 1.7mg/dl;
  - ALT, AST, GGT ≥3 times the upper limit of normal or ALT-to-AST ratio ≥2.0;
  - TBIL >20.0 mg/dl and DBIL ≥ 4.0mg/dl;
  - LDH > 400U/L;
  - K+<3.2mmol/l and >5.3mmol/l, Na+<132mmol/l and >147mmol/l, Ca+2<1.05mmol/l and >1.40mmol/l;
- A complete urinalysis should not reveal:
  - Gross hematuria or clinically significant microhematuria - >25 erythrocytes/field of view;
  - Clinically significant proteinuria - >300 mg/dl or albumin-to-creatinine ratio >300 mg/g;

Screening tools are required for the initial clinical evaluation and the study baseline data generation. Diagnostic tests that are used for baseline clinical evaluation are regularly applied in everyday, real-life clinical practice for routine observation of patients with the clinical features of interest.

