#### **2.4.4 Exclusion Criteria**

Exclusion criteria are defined as diseases, clinical conditions, risks or treatment limitations, and contraindications that increase the severity and risks of the study cases. These conditions may have

additional negative prognostic effects on the study subject's disease/condition, interfere with the development of study endpoints, or alter the effectiveness of the treatment interventions included in the study.

Exclusion criteria are used to identify and exclude potential study participants with clinical severity characteristics to ensure homogeneity of treatment effects. They also prevent bias, confounding, and unintended effects.

The use of criteria ensures the safety of subjects in the study by identifying diseases/conditions that require clinical observation, evaluation, and treatment measures other than those specified in the study.

Any of the following should be considered as exclusion criteria from the study:

- Concomitant using of potent CYP3A4 or CYP2C19 inhibitors;
- Clinical obesity, BMI - 40 kg/sq.m or more;
- Type 1 diabetes mellitus;
- Poorly controlled type 2 diabetes mellitus, Hba1c - 9% or more;
- Acute Myocardial Infarction;
- Coronary artery bypass grafting was performed within the last 12 weeks.
- Valvular heart disease due to dysplasia, connective tissue disorders, or inflammatory disorders, or valvular disorders requiring cardiac surgery;
- History of severe hepatic impairment;
- Severe chronic kidney disease;
- Clinically important leucopenia, lymphopenia, thrombocytopenia or thrombocytosis;
- History of hemorrhagic diathesis or coagulopathy;
- An active or an obvious threat of bleeding (including GI bleeding):
- Bleeding within the past 6 months that required hospitalization;
- Blood transfusion during the past 6 months or its refusal;
- History of intracranial hemorrhage;
- Cardiac or non-cardiac degenerative disease, including: cardiomyopathy, restrictive lung disease, or neurodegenerative diseases;
- Malignant tumor (cancer) that limits life expectancy to less than one year;
- Current chemotherapy or immunosuppressive therapy;
- Ongoing immunosuppression or immunosuppressive conditions;
- Pregnancy or lactation period;
- Any disease/condition for which control is not achieved;
- Personal (patient/physician dependent) or health care system-related circumstances that can restrict or limit any study procedures or operations.

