Hemorrhagic diathesis, coagulopathy, significant bleeding within the past 6 months, blood transfusion within the past 6 months (or refusal of blood transfusion), active gastrointestinal bleeding or threat of bleeding, and a history of intracranial hemorrhage pose clinical conditions that determine a high risk of recurrent bleeding complications. Therefore, these conditions carry an obvious threat of recurrent bleeding events during treatment with P2Y12 inhibitors, clopidogrel or alternatives, due to inhibiting platelet aggregation. Platelet inhibition occurs throughout their life cycle (7-10 days), and in the event of bleeding, simply stopping the drug will not have a significant effect on pro-coagulation treatment. However, due to the short half-life of the active metabolite of clopidogrel, hemostasis can be restored by infusion of exogenous platelets. The effects of platelet transfusion are significantly reduced within 4 hours of a loading dose of clopidogrel and within 2 hours of a maintenance dose.

When conducting antiplatelet therapy with clopidogrel, prasugrel or ticagrelor, it is necessary to take into account the following conditions that are not direct contraindications, but which nevertheless determine important limitations.

After surgical operations, the expected antiplatelet effects in response to treatment with P2Y12 inhibitors are undesirable. Therefore, treatment with P2Y12 inhibitors should be discontinued at least 5 days before surgery and should be resumed as soon as the operative risk of bleeding has decreased.

In patients with moderate and severe renal insufficiency (creatinine clearance from 30 ml/min to 60 ml/min and <30 ml/min, respectively), clopidogrel reduces the effects of ADP-induced platelet aggregation by an average of 25%. Such effects are associated with an increased risk of thrombosis despite clopidogrel treatment. Increasing the dose of clopidogrel to reduce the risk of thrombotic complications is unreasonable and significantly increases the risk of bleeding and TTP. Therefore, cases of moderate and severe chronic kidney disease are exclusion criteria from the study.

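### Section 2.5.1 prints a haematocrit limit that every patient meets and an eGFR limit in an invalid unit; its bilirubin limits are probably a unit error for the sponsor to confirm

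*Combined protocol and SAP*

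**What the plan says.** Section 2.5.1 (Screening) says that screening examinations should not identify the conditions excluded in section 2.4.4, or certain laboratory findings, and then lists numerical limits. Four lines matter here, with a fifth used for comparison.

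- Blood count: "Clinically significant anemia - Hb<10g/dl; RBC<3.5; HCT<32L/L". Semicolons separate the three values, with no *and* or *or*. The RBC value has no unit.
- Liver enzymes: "ALT, AST, GGT ≥3 times the upper limit of normal", with an ALT-to-AST ratio as an alternative.
- Bilirubin, on the next line: "TBIL >20.0 mg/dl and DBIL ≥ 4.0mg/dl".
- Kidney function: "eGFR ≤30% (according to the MDRD formula for kidney disease", with a creatinine limit as an alternative.
- Potassium, for comparison: below "3.2mmol/l and >5.3mmol/l".

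The section 2.4.4 list includes "Clinically important leucopenia, lymphopenia, thrombocytopenia or thrombocytosis" and "History of severe hepatic impairment" but not anaemia. Its explanatory text extends the liver exclusion to clinically significant liver disease, and describes renal insufficiency by "creatinine clearance from 30 ml/min to 60 ml/min" for the moderate range. Nothing elsewhere restates or corrects the haematocrit or bilirubin limits, and no normal range for bilirubin is given.

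**The concern.** These are operative eligibility thresholds, and section 2.5.7 relies on strict application of the criteria to make the arms comparable. A limit that cannot be applied literally leaves each site or monitor to correct it unaided. Section 2.5.1 is also the only place where the plan sets a limit for anaemia, in a trial of antiplatelet drugs where bleeding risk drives many exclusions.

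The two main errors behave differently. The haematocrit limit is impossible and would be noticed at the first blood count. The bilirubin limit can be applied but is lenient, so the line itself would not alert anyone. The eGFR unit is a third slip in the same list.

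**Working it through.** There is no figure of the plan's own to reproduce. The check is one of units and multiples. The documents give no normal bilirubin limits, MCHC or MCV; all values for these below are assumptions, shown as ranges.

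**Haematocrit**

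1. L/L is volume of cells over volume of blood, so the maximum is 1. Since 1 < 32, the condition is true of every patient.
2. If any one anaemia value is enough, everyone is excluded. If all three are required, the haematocrit term never changes the result.
3. Check of 32% against its neighbours:
   - From Hb 10 g/dl, haematocrit = Hb / MCHC. With MCHC 31-36 g/dl: 10/36 = 0.28 to 10/31 = 0.32 L/L.
   - From RBC 3.5 (assumed ×10¹²/L), haematocrit = RBC × MCV. With MCV 80-100 fl: 3.5 × 0.080 = 0.28 to 3.5 × 0.100 = 0.35 L/L.
4. A limit of 0.32 L/L fits both neighbours. The printed number is 32/0.32 = 100 times that.

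**eGFR**

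The MDRD formula returns a filtration rate in volume per unit time, not a percentage. Section 2.4.4 grades renal insufficiency in ml/min.

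**Bilirubin**

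1. Multiple of normal = printed limit / assumed upper normal limit.

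| Limit (mg/dl) | Assumed upper normal (mg/dl) | Multiple |
|---|---|---|
| Total 20.0 | 1.0 to 1.3 | 20 to 15.4 |
| Direct 4.0 | 0.2 to 0.4 | 20 to 10 |
| Direct 4.0 | 0.5 | 8 |

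2. The enzyme limit is 3 times normal. On that scale the bilirubin limits are looser by 8/3 = 2.7 to 20/3 = 6.7 times.
3. The connector: no potassium value can be both below 3.2 and above 5.3 mmol/l, so *and* on that line must mean *or*. The *and* between the bilirubin limits is therefore ambiguous.
4. An example under both readings: total 10 and direct 3.5 mg/dl. Since 10 is not above 20.0 and 3.5 is below 4.0, the patient passes this line under *and* and under *or*. The values are 10/1.3 = 7.7 to 10/1.0 = 10 times (total) and 3.5/0.5 = 7 to 3.5/0.2 = 17.5 times (direct) the assumed normal limits.
5. One possible explanation: at 17.1 µmol/l per mg/dl, 20 µmol/l = 20/17.1 = 1.17 mg/dl and 4 µmol/l = 4/17.1 = 0.23 mg/dl. Both fall within the assumed ranges for the upper normal limit. That fits µmol/l having been mislabelled as mg/dl, but does not prove it.

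**The case against.** **Any clinician would read 32%.** Probably so. The value sits on a line about anaemia, after a haemoglobin limit that it matches, and only one correction suggests itself. A reader might infer from the literal text that the trial could enrol nobody; the documents do not support that as a practical outcome, since the values may be meant jointly and no site would act on the other reading. The printed limit is still wrong. A decimal point lost when the PDF was read cannot be wholly excluded, but other decimals in the same list survived.

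**The bilirubin limits are a choice of strictness.** This stands in part. The limits can be applied as printed, every multiple rests on an assumed normal value, and nothing requires bilirubin and enzymes to share a multiple. A reader might infer that the bilirubin values are demonstrably wrong; the documents do not show that. The eGFR slip shows loose drafting in the list, not that the bilirubin line is misprinted. What remains is that the multiple stays at 8 or more across the assumed range, which is hard to explain as deliberate beside a limit of 3.

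**Other safeguards apply.** They do. Severe hepatic impairment, clinically significant liver disease and any uncontrolled disease are excluded in section 2.4.4, and the enzyme, platelet and coagulation limits in section 2.5.1 still operate. The example patient passes the bilirubin line only; an investigator would have to overlook those exclusions to enrol that patient. Appendix 2 schedules a blood count at screening but does not itemise bilirubin, so how that limit works in practice is less certain. A reader might infer that patients with liver failure would enter the trial; the plan as a whole does not support that.

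**Conclusion.** The haematocrit limit is wrong as printed. That follows from the unit alone, and confidence is high. That 0.32 L/L was intended rests on the assumed MCHC and MCV, but the agreement with both neighbouring values is close. The eGFR unit is invalid.

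The bilirubin limits are probably a unit error, with medium confidence: about 15-20 times normal for total and 8-20 times for direct, assuming upper normal limits of 1.0-1.3 and 0.2-0.5 mg/dl. The intended values and connector cannot be recovered from the documents.

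Severity is minor. The safety effect is small given the overlapping exclusions. The limits act before randomisation and identically for all candidates, so a reader should not infer bias between arms; sample size, power and analysis are untouched.

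**What to change.** Correct three lines of section 2.5.1 in one edit:

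- **Haematocrit:** print <0.32 L/L (32%), and state whether any one of the three anaemia values excludes or all are needed.
- **eGFR:** replace the percentage with the unit that the MDRD formula returns.
- **Bilirubin:** the sponsor confirms the intended unit and whether the limits are joined by *and* or *or*, then restates them, for example as multiples of the upper limit of normal. The choice of values and connector is the sponsor's.

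If the database validation mentioned in sections 2.5.7 and 7.1 includes range checks on these variables, match them to the corrected units. If screening is already over (section 7.2 anticipated final primary-outcome data collection in April 2025), record which limits the sites actually applied. The cost is a wording correction and any matching database checks, with no extra patients or tests.
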